(2) To develop, using a mixed methods approach, a targeted educational intervention about prostate cancer for men who live in high risk neighborhoods

No hypothesis is being tested for this aim.

(3) To test the impact of the targeted intervention on levels of knowledge, anxiety, and informed decision making about PCa screening

Hypothesis 3a: Men in the prostate-specific intervention group will have higher levels of knowledge about PCa screening than those who receive the healthy lifestyle control intervention

Hypothesis 3b: Men who express a greater number of barriers to PCa screening will have higher levels of anxiety about PCa and PCa screening

Hypothesis 3c: Men in the prostate-specific intervention group will have higher levels of informed decision making about PCa screening than those who receive the healthy lifestyle control intervention

Sub-aim: To examine if there are differences in outcomes by intervention setting

(4) To observe the rates of PCa screening in the intervention and control groups

B. RESEARCH STRATEGY

B.1. Experimental Design

The proposed design is a mixed-methods study including quantitative analyses of state registry data, survey data and Philadelphia health statistics, qualitative analyses of focus group results, and the test of a targeted intervention to improve key factors associated with shared decision making and potential uptake of prostate cancer screening in high-risk neighborhoods. Table 2 provides a brief summary of the study populations, study outcomes, traits to be measured, and analytical methods proposed to accomplish each specific aim.

Table 2: Summary of Specific Aims and Study Methods

	Aim 1: Identify high risk neighborhoods	Aim 2: Develop intervention via mixed-methods approach	Aim 3: Test intervention in high risk neighborhoods
Sample Population	Estimates from 1995-2005 data: ~4,500 African-Amer. cases ~4,000 European Amer. Cases		200 At-Risk Men
Primary Outcomes	Prostate cancer mortality; tumor stage and grade		Prostate cancer knowledge, anxiety, intention to screen, PSA screening
Neighborhood Data	Demographics, PCa screening, other health behaviors, health conditions, SES		
Patient-Level Data	Race, age, marital status	Focus Group Results	

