The CHDB is a random digit dial telephone survey of more than 10,000 households biannually to examine the health and social well-being of residents in the Greater Philadelphia Region. The survey is conducted as part of Philadelphia Health Management Corporation's (PHMC) CHDB, which contains information about local residents' health status, use of health services, and access to care. PHMC is a nonprofit, public health organization committed to improving the health of the community through outreach, education, research, planning, technical assistance, and direct services.

The most recent CHDB survey was conducted in 2012 and included questions about PCa screening, other health screening, utilization of healthcare services, health insurance, barriers to care, neighborhood factors (nearby parks and social capital), and lifestyle factors. The survey's response rate averages about 30% over the years. The CHDB also maintains U.S. Census and all-cause mortality data. These data can be examined by different levels of geography, including census tract, health district, Minor Civil Division, and ZIP code, as well as by county and region.

B.2.d. General Analytical Considerations

After the completion of data entry and data checking, a series of standard exploratory data examination steps will be undertaken before the formal analytical methods are applied. First, exploratory analyses will be undertaken to identify any data errors or inconsistencies. This will include generating plots of frequency distributions of all measured traits to identify outlier points that may be outliers or data errors. The distributions of the variables will also be checked to insure that the assumptions of the analytical methods to be applied are not violated. Transformations of the data to normality will be made based on the outcome of these exploratory steps if necessary. Once these exploratory steps have been completed, descriptive statistics will be computed. Continuously distributed variables will be summarized by estimating values of the mean, median, and standard deviation, and by determining the range of the observed values. Variables with a discrete distribution will be summarized by frequencies and standard deviations. STATA/SE 13.1 and SAS version 9.4 will be used to analyze the data for the completion of this study. P-values less than 0.05 will be considered statistically significant.

Figure 2: A Map of Philadelphia Neighborhoods

B.2.e. Aim 1 Analytical Methods

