Informed Consent and Baseline Survey: The health educator will obtain informed consent from each participant by reviewing the consent document and answering any questions about the study. After signing the consent document, participants will complete a brief pencil-and-paper baseline questionnaire. Items to be assessed at baseline include knowledge about prostate cancer and screening, attitudes towards screening, subjective norms about screening, decisional conflict about screening, and intentions to screen. Knowledge about prostate cancer and screening will be measured with a 17-item scale, recently validated with a sample of African American males. [18] The measure for decisional conflict will be constructed from O'Connor's Decisional Conflict Scale, a frequently used assessment for anxiety about decision making.[19] This scale includes a self-efficacy subscale that pertains to whether the participant feels 'a lot confident', 'a little confident', or 'not at all confident' about making an informed health decision. Demographic data related to age, race/ethnicity, family history of prostate or other cancer, and other pertinent health information will be collected. Additionally, contact information (telephone number(s), email address, and mailing address) for each participant will be collected to aid in maintaining communication with enrolled participants for post-survey completion.

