Study Intervention: Men who live in the Intervention Group Neighborhoods: After obtaining informed consent and administering the baseline survey, the health educator will show the short introductory video on a tablet computer. Then, the educator will use the curriculum booklet, one given to each participant, to review general information about the prostate gland, prostate incidence and development, risk factors, screening options, screening guidelines and the importance of repeat screening.[20] The educational session is meant to be interactive, with men feeling comfortable to ask questions and engage in a discussion with the educator and the other men at the session. Men Who Live in the Control Group Neighborhoods: After obtaining informed consent and administering the baseline survey, the health educator will show the short introductory video on a tablet computer. Then, the educator will use the curriculum booklet, one given to each participant, to review topics about health promotion actions related to diet, exercise, tobacco, general cancer screening and cardiovascular risk. The educational session is meant to be interactive, with men feeling comfortable to ask questions and engage in a discussion with the educator and the other men at the session. It is anticipated that the educational sessions for both groups will last about 15 minutes.

Post-Survey(s): Immediately following the intervention, men will complete a brief paper-and-pencil endpoint survey. The majority of items on the baseline survey, except for the demographic and contact information, will be repeated on the endpoint survey. Additionally, the study research assistant will call each enrolled participant at 1 month and 4 months after their enrollment date to administer the same endpoint survey. Participants who are not reached by telephone will be contacted by mail and by email to attempt to retain the maximum number of participants over time.

Participant Compensation: Participants will be compensated \$25.00 after completing the endpoint survey on the day of the intervention and \$25.00 for the completion of each follow-up survey.

Referral to Screening

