The target sample size is $n=200$ men. Since we anticipate 20% attrition, we will recruit and consent 240 evenly distributed across each of the 4 neighborhoods. In a local population similar to our target population, a previous prostate cancer screening decision making study [21] found that, compared to standard intervention controls, their decision support enhanced intervention lead to a 0.8 point increase ($SD = 1.5$) in knowledge on a 10-point scale. Assuming this in our target population, a type I error rate of 0.05, an intra-neighborhood correlation of 0.005 to 0.01, and that 4 to 10 neighborhoods will be sampled per group, the planned study should have approximately 80% to 94% power to detect this difference. In a similar prostate cancer screening shared decision making article [22], investigators found that their intervention lead to a 22% reduction ($SD = 0.15$) in prostate screening. Making similar assumptions as for the knowledge endpoint, we may be somewhat underpowered for detecting this difference in screening rates as the expected power would be approximately 50% to 67%. However, the primary goal is to increase knowledge about screening so that each man will make an informed decision taking into account his risk factors and personal preferences.

B.4.f. Results Dissemination

The study results will be disseminated to the neighborhood at the end of the project by multiple methods. Town hall meetings will be held in the targeted neighborhoods to explain the goals of the study and to provide a summary of results and additional PCa education to the community at-large. Next steps will be discussed, as well as ways to improve, sustain and expand targeted educational interventions around the Philadelphia region. Project newsletters and brochures will be made available to be shared with family and community members. The video developed during aim 2 for educational purposes will be shared at the town halls and will be made available on the internet for public education.

C. Potential Problems and Alternative Approaches

C.1. Geocoding

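### Aim 3 lists four unranked primary outcomes that conflict with the hypotheses and the power section, and names no primary time point and no multiplicity rule

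*Combined protocol and SAP*

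**What the plan says.** Four parts of the document bear on what Aim 3 will be judged by.

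- **Table 2 (B.1)** gives the primary outcomes for Aim 3 as "Prostate cancer knowledge, anxiety, intention to screen, PSA screening". There is no order among them.
- **Aims and hypotheses (A.1).** 3a compares knowledge between groups. 3b relates anxiety to the number of barriers a man reports, not to study group. 3c compares informed decision making between groups. Aim 4 is "To observe the rates of PCa screening in the intervention and control groups" and carries no hypothesis.
- **Surveys (B.4.c).** The baseline survey covers knowledge (a 17-item scale) and "attitudes towards screening, subjective norms about screening, decisional conflict about screening, and intentions to screen". After the session, "Immediately following the intervention, men will complete a brief paper-and-pencil endpoint survey", repeating most of the baseline items. A research assistant then calls each man "at 1 month and 4 months after their enrollment date to administer the same endpoint survey".
- **Decision rule.** B.2.d states "P-values less than 0.05 will be considered statistically significant". B.4.e powers the knowledge comparison at "a type I error rate of 0.05" and adds that "the primary goal is to increase knowledge about screening so that each man will make an informed decision".

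B.4.d says that mixed models will test the hypotheses, but names no outcome, time point, testing order or adjustment for multiple tests. It leaves the choice of specific models and confounders until descriptive statistics have been seen.

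**The concern.** A reader of the final report could not tell from the plan which comparison was meant to decide whether the intervention worked. Table 2, the hypotheses and the power section each point to a different set, and any of three surveys could supply the result. With a flat 0.05 for every test, the error rate for the trial's main conclusion is above 0.05 as soon as more than one comparison can carry it. The outcome and survey that carry it could also be settled after the data are seen.

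The immediate survey makes this more than formal. It is completed straight after a session of about 15 minutes that, in the intervention neighborhoods, teaches about prostate cancer and screening. A difference in knowledge at that moment may reflect recall alone. Nothing in the plan prevents it from standing as the trial's result.

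**Working it through.** **1. The plan's own figure.** The document states no family-wise error rate. Its only related figure is the power for knowledge, 80% to 94%. Inputs from B.4.e: difference 0.8, SD 1.5, n = 200 (100 per group), intra-neighborhood correlation (ICC) 0.005 to 0.01, and k = 4 to 10 neighborhoods per group. I took the test as two-sided, since B.4.e does not say.

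- Design effect DE = 1 + (100/k − 1) × ICC
- Noncentrality = 0.8 / (1.5 × √(2 × DE/100)), with a t test on 2(k − 1) degrees of freedom
- k = 4, ICC 0.01: DE = 1.24, noncentrality 3.39, 6 df, power 80.4%
- k = 10, ICC 0.005: DE = 1.045, noncentrality 3.69, 18 df, power 93.7%

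The stated range is reproduced, and it is power for a single knowledge test at 0.05.

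**2. The lists side by side.**

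| Outcome | Table 2 | Between-group hypothesis | Listed survey item |
|---|---|---|---|
| Knowledge | primary | 3a | yes |
| Anxiety | primary | none (3b concerns barriers) | decisional conflict |
| Intention to screen | primary | none | yes |
| PSA screening | primary | none (Aim 4 observes) | not listed |
| Informed decision making | absent | 3c | no measure of that name |

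Only knowledge appears in all three columns.

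**3. Chance of at least one p < 0.05 when no effect exists.** For m independent tests this is 1 − 0.95^m.

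| Family | m | Chance |
|---|---|---|
| 3a and 3c, one time point | 2 | 9.75% |
| Knowledge alone, three surveys | 3 | 14.3% |
| Four Table 2 outcomes, one time point | 4 | 18.5% |
| 3a and 3c, three surveys | 6 | 26.5% |
| Table 2 outcomes at three surveys, without PSA at the immediate one | 11 | 43.1% |
| Four Table 2 outcomes, three surveys | 12 | 46.0% |

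**4. Correlation.** The document gives no correlations, so these are assumed values applied to two-sided tests on jointly normal statistics.

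- Two tests, from 1 − P(|Z1| ≤ 1.96 and |Z2| ≤ 1.96): 9.5% at correlation 0.3 and 8.3% at 0.7.
- Four tests, by simulation: 17.5% at 0.3 and 13.0% at 0.7.
- Twelve tests, by simulation: 35.6% with correlation 0.5 both between outcomes and between surveys; 24% with 0.7 between outcomes and 0.8 between surveys.

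The rate falls to 5% only as the tests become identical.

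**5. What different remedies cost in power.** A single primary test at 0.05 leaves step 1 unchanged. Bonferroni over four outcomes (0.05/4 = 0.0125 each) cuts knowledge power to 51% (k = 4, ICC 0.01) and 81% (k = 10, ICC 0.005).

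**The case against.** The strongest reply is that the plan already has a primary outcome in substance. B.4.e gives knowledge priority, rests the main power claim on it and concedes low power for screening. Table 2 is introduced only as a brief summary. The formal hypotheses contain just two between-group comparisons, 3a and 3c. Both are directional: counting only results that favor the intervention, two independent two-sided tests give 1 − 0.975² = 4.9%.

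Much of this stands. Knowledge has informal priority, and two tests at one time point is the narrowest fair reading. It does not close the gap. The sentence in B.4.e states a purpose and names no survey, and Table 2 contradicts it. B.4.e also gives power (50% to 67%) for a difference in screening rates, which suggests a test of an outcome that Aim 4 only observes. The 4.9% is about twice the 2.5% that one such test would give, and it rises to 1 − 0.975⁶ = 14.1% if both hypotheses are tested at all three surveys.

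A reader might go further and infer that all four outcomes are measured and tested at each of three surveys. The documents do not say so. PSA uptake is not a listed survey item, an immediate survey cannot capture screening prompted by a session that has just ended, and no per-survey test is described.

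**Conclusion.** The gap is real and worth correcting before analysis. The primary outcomes of Aim 3 are not consistently defined, no time point is primary, and there is no multiplicity rule. On the narrowest reading the chance of at least one false positive is 9.75%. It is 18.5% on the face of Table 2 at one time point and 26.5% for 3a and 3c at all three surveys. The 46% for 12 tests (43% for 11) is a ceiling for the Table 2 outcomes, not an estimate.

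These figures assume independence, a true 5% level for each test and no effect on any outcome. Correlation reduces them; at the values examined none reaches 5%.

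A reader might conclude that a chance positive trial is more likely than not. That does not follow: every figure is below one half, and the plan defines no rule by which one p below 0.05 makes the trial positive.

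**What to change.** Amend Table 2 and B.4.d so that the 17-item knowledge score at one pre-named follow-up time is the sole primary outcome, tested at 0.05. Four months is a reasonable choice because it tests retention rather than immediate recall. The document does not dictate 4 months over 1 month, so the sponsor should confirm it.

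Make all other outcomes and time points secondary, with Holm adjustment or with estimates and confidence intervals only. Bring Table 2, hypotheses 3a to 3c, Aim 4 and B.4.e into agreement. That includes naming the measure for informed decision making and saying how and when PSA screening is ascertained.

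The cost is wording, and secondary outcomes lose unadjusted significance claims. Power for knowledge stays at the stated 80% to 94% on the plan's own inputs.

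This deals with multiplicity only. It does not address error from having two non-randomized neighborhoods per arm. Nor does it resolve the power calculation's assumption of 4 to 10 per group; with two per group, the method in step 1 gives 40% to 46%.

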A Neighborhood Based Intervention to Reduce Prostate Cancer Disparities

NCT # 03197896

Date: May 28, 2015

A. BACKGROUND

Prostate cancer (PCa) is the most prevalent malignant cancer among men in the U.S. and 233,000 cases are expected in 2014.[1] Although PCa survival has improved over the years via PSA testing and early treatment, socioeconomic (SES) and racial disparities persist in the US.[2] Highest mortality rates for PCa have been observed for African Americans and men living in high poverty areas. [1, 2] Surveillance, Epidemiology and End Results (SEER) data indicate that late stage diagnosis has been associated with low SES across cancers.[3] In a meta-analysis, studies adjusting for SES and clinical factors show that while racial differences in all-cause mortality decrease, differences in prostate cancer recurrence and prostate-specific mortality persists.[4] These disparities are believed to be a result of interactions among genes, health behaviors, and environmental factors. Developing strategies that will eliminate these disparities and lay the ground work for reducing other health disparities requires multidisciplinary approaches.

A.1. Specific Aims and Hypotheses

Building on our previous research on the complex etiology and progression of PCa, we propose to develop and test the effects of a targeted intervention focused on increasing decision making about PCa screening compared to a healthy lifestyle intervention. We will build on substantial resources developed over the last fifteen years at two collaborative institutions in inner-city Philadelphia to understand the contribution of residential environment and neighborhood-level barriers to early PCa screening and later clinical manifestation of the disease.

Specific aims of the study are:

(1) To identify neighborhoods with disproportionately high rates of advanced prostate cancer and describe patient- and neighborhood-level risk factors associated with the high risk neighborhoods

Hypothesis 1a: Neighborhoods with the highest prevalence of advanced PCa will also present with poor prostate-specific survival compared to other neighborhoods.

Hypothesis 1b: Neighborhoods with the highest prevalence of advanced PCa will have a higher prevalence of risk factors including older age at diagnosis, African American residents and low neighborhood SES compared to other neighborhoods.

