Major Analytical Approaches	Descriptive analyses (t-tests, frequency tables, nonparametric tests), Correlations, Trend tests, EpiQMS (online tool), GIS mapping	Thematic coding	Descriptive analyses (t-tests, frequency tables, nonparametric tests), Correlations, Regression Models

B.2. Aim 1: To identify neighborhoods with disproportionately high rates of advanced PCa and describe patient- and neighborhood-level risk factors associated with the high risk neighborhoods

To address Aim 1, we will use data from the Pennsylvania State Cancer Registry to select four neighborhoods in Philadelphia with the highest population-adjusted rates of late-stage PCa and the lowest rates of PCa screening. This will provide the research team with 4 neighborhoods with the highest concentration of men who are at risk for poor PCa outcomes in Philadelphia. We will also analyze data from the 2010 U.S. Census and Philadelphia's Community Health Database (CHDB) to identify additional insights about the characteristics of the 4 selected neighborhoods. In addition to collecting self-reported health outcomes, the CHDB conducts annual surveys of residents' cancer screening behavior, healthcare utilization, access to care, and demographic information.

B.2.a. PA Cancer Registry Data

[name] will obtain updated anonymized cancer registry PCa data for Philadelphia (5 most recent years) from the Pennsylvania Department of Health, including patient addresses, age, race, marital status, tumor stage and grade and treatment type

EpiQMS (Epidemiologic Query and Mapping System) is a new interactive tool available on the PA Health Department Website to compute disease rates and generate general maps for various diseases and health outcomes. Output includes age-adjusted and age-specific rates. Most output can also be broken down for various demographics such as age, sex and race/ethnicity. Maps include rates based on Bayes smoothing techniques and on nearest neighbor calculations to diminish the negative effects of small numbers.

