State Cancer Registry Outcome Variables. Our primary outcome variables will be indicators of prostate cancer severity that are associated with differences in long-term survival. [5] These variables include tumor stage, with low stage defined as stages 1 and 2 (localized disease) and high stage is defined as stages 3 and 4 (non-localized.); tumor grade, with low grade is defined as tumor Gleason score of 6 or below and high grade is defined as a tumor score of 7 or greater; and tumor aggressiveness, defined as a combined high tumor stage (stage 3 or 4) and high tumor grade (grade 7+) compared to those with other combinations of these variables. High risk neighborhoods will be defined as census tracts in Philadelphia with highest incidence rates of advanced prostate cancer at diagnosis (PCa Gleason score ≥ 7 and/or tumor stage III/IV.)

B.2.b. Geocoding Methods

Patient addresses will be geocoded using ArcGIS and methods outlined by The Public Health Disparities Geocoding Project. [6] We will geocode patient addresses to determine the Philadelphia neighborhoods, at the census tract level, with the highest population-adjusted PCa rates. Census tracts are one of the preferred area-based units to use when attempting to capture economic deprivation. Census tract (and smaller block-group) boundaries are intended to combine individuals that tend to be similar with regard to social and economic characteristics. [7] Census tracts are U.S. Census Bureau defined, standardized, and relatively permanent geographical units. They are constructed specifically to include on average 4,000 people of fairly homogeneous population characteristics, economic position, and living conditions. [8] We will map population-adjusted rates of advanced prostate cancer, screening rates, and other demographics by neighborhood census tract. We will use these maps to select the 4 neighborhoods with the highest risk of PCa morbidity and mortality in Philadelphia. Adjacent high risk census tracts that fall into a given Philadelphia neighborhood will be considered part of one high risk neighborhood and will be used to recruit men into focus and intervention groups for aims 1 and 2 of this proposal.

B.2.c. Description of the CHDB

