Descriptive analyses will be conducted to characterize high risk PCa census tracts compared to lower risk census tracts. Mapping the high risk census tracts will help us to determine how they are distributed within and around pre-defined Philadelphia neighborhoods (commonly used community names for each section of the city, Figure 2.) Those Philadelphia neighborhoods will become the target

neighborhoods for aims 2 and 3. Continuous variables will be analyzed with t-tests (or nonparametric alternative tests for variables without normal distributions) and categorical variables will be analyzed with frequency tables and chi square tests or Fisher's exact tests if any expected cell frequencies are small. Patient-level and neighborhood variables will be summarized for comparisons between high risk and lower risk neighborhoods to highlight factors that may be central topics of focus groups and intervention development. Correlations will be computed to examine the relationship between percent of cases with advanced disease and prostate-specific mortality rates. Regression modeling will allow us to determine significant trends in PCa incidence and mortality over time with and without adjustment for covariates such as the prevalence of risk factors including older age at diagnosis, African American residents and low neighborhood SES. We will also use the EpiQMS tool provided on the PA Department of Health website to determine age-specific incidence and mortality rates for Philadelphia. Generating maps of these data along with maps showing highest prevalence of PCa screening (CHDB data) will indicate where should target our focus groups and interventions for aims 2 and 3.

B2.f. Designation of Neighborhoods for Study Condition

Based on the GIS mapping results, the four neighborhoods in Philadelphia with the highest rates of late-stage PCa will be chosen to serve as study sites. Study condition (intervention or control) will be designated at the neighborhood level. Therefore, two of the sites will be designated as intervention neighborhoods and two will be designated as control neighborhoods. All men who live in the same neighborhood will receive the same intervention. All efforts will be made to ensure that the designations are done in a way that Intervention and Control neighborhoods are not geographically adjacent to each other, to avoid contamination of study messages among participants.

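### Aim 1 sorts census tracts by tumor stage and grade, so p-values for stage, grade or aggressiveness between the resulting groups are circular; the Hypothesis 1a correlation needs its source of deaths stated

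*Combined protocol and SAP*

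**What the plan says.** Section B.2.a sets the grouping rule: "High risk neighborhoods will be defined as census tracts in Philadelphia with highest incidence rates of advanced prostate cancer at diagnosis". Advanced disease is defined there as "PCa Gleason score ≥ 7 and/or tumor stage III/IV". The same paragraph says: "Our primary outcome variables will be indicators of prostate cancer severity that are associated with differences in long-term survival", and lists them as stage, grade, and aggressiveness (high stage and high grade together). Table 2 gives the Aim 1 primary outcomes as "Prostate cancer mortality; tumor stage and grade".

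Section B.2.e compares high-risk with lower-risk tracts, using t-tests or nonparametric tests for continuous variables and chi-square or Fisher tests for categorical ones. B.2.d adds: "P-values less than 0.05 will be considered statistically significant". No section separates the data used to form the groups from the data used to compare them.

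Hypothesis 1a (A.1) reads: "Neighborhoods with the highest prevalence of advanced PCa will also present with poor prostate-specific survival compared to other neighborhoods". The matching analysis in B.2.e is: "Correlations will be computed to examine the relationship between percent of cases with advanced disease and prostate-specific mortality rates".

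**The concern.** If areas are ranked on a variable and the top ones are compared with the rest on that same variable in the same cases, a difference is guaranteed by the ranking. Chance excesses of advanced cases land in the high-risk group by design. An ordinary chi-square test takes no account of this, so its p-value does not separate real neighborhood differences from noise. Aim 1 asks whether advanced disease is concentrated in particular places, so a reader would naturally take a small p-value for stage or grade as support.

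Hypothesis 1a raises a related but separate question. Men with advanced disease die of it more often. If deaths are counted among the cases that supply percent advanced, an area with more advanced cases by chance will tend to show more deaths by chance, and the two will correlate even when the areas do not differ.

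**Working it through.** **Inputs from the documents.** Table 2 gives about 4,500 + 4,000 = 8,500 cases for 1995-2005, which is 11 years. B.2.a requests 5 years: 8,500 × 5/11 ≈ 3,864 cases. The threshold is 0.05, taken as two-sided. The plan gives no Aim 1 power figure to reproduce.

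**Assumptions not in the documents.** 20 to 380 areas of equal population; 4 to 38 flagged as high risk; 30% or 50% of cases advanced; stage III/IV in 35% of advanced cases; prostate-cancer death 15% if advanced and 3% (or 2% where stated) if not.

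**Hand check, all areas identical, 380 tracts, 38 flagged, 50% advanced.**
- Cases per tract: 3,864/380 = 10.17, so 5.08 advanced and 5.08 not. Poisson SD of the advanced count: √5.08 = 2.25.
- The top tenth of a normal distribution averages 1.755 SD above the mean: 5.08 + 1.755 × 2.25 ≈ 9.04 advanced per flagged tract. The non-advanced count stays at 5.08.
- Percent advanced, flagged: 9.04/14.12 = 64.0%. Others: (5.08 − 0.1 × 9.04)/0.9 = 4.64 advanced, and 4.64/9.73 = 47.7%.
- Gap ≈ 16.3 points. Cases: 38 × 14.12 ≈ 537 and 342 × 9.73 ≈ 3,327. Standard error = 0.5 × √(1/537 + 1/3,327) = 0.0233, so z ≈ 7.0 with no true difference.

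**Simulation, all areas identical, 1,500 runs per setting.** Ranges cover 30% and 50% advanced. The last column correlates percent advanced with deaths per case in the same cases (15% vs 3%).

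| Areas / flagged | False gap (points) | Advanced status p<0.05 | Stage III/IV p<0.05 | H1a correlation p<0.05 |
|---|---|---|---|---|
| 380 / 38 | 17-20 | 100% | 93-100% | 98% |
| 200 / 20 | 13-15 | 100% | 70-93% | 84-89% |
| 100 / 10 | 10-11 | 99-100% | 41-67% | 58-62% |
| 50 / 4 | 7-8 | 78-94% | 22-36% | 31-35% |
| 20 / 4 | 4-5 | 55-77% | 16-25% | 13-16% |

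Grade alone and aggressiveness were not simulated; the same mechanism applies because both are built from the sorting variables.

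**What is not inflated.** Race and an area SES score, simulated as unrelated to stage, were significant in 4-6% of runs. Age at diagnosis was not simulated; it would be affected only if related to stage.

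**Hold-out for the group comparison.** With areas selected on independent data, 38 of 380 gave 5.6% (advanced status) and 5.1% (stage); 4 of 50 gave 6.1% and 5.7%.

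**Hypothesis 1a.** Independent selection leaves the correlation where it was (97.9% with 380 tracts, 32.7% with 50 areas), so the grouping is not its cause. Removing the stage-death link brings it to 7% with 380 tracts. At 15% vs 2% death it is about 99% with 375 tracts, 60-64% with 100 areas and 32-38% with 50; at 8% vs 2% with 375 tracts, 73-76%. Taking percent advanced from one half of the cases and deaths from the other half gives 4-6%.

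**The case against.** **The test is not spelled out.** B.2.e calls these analyses descriptive, uses them partly to choose focus-group topics, and does not name stage or grade as variables to be tested. Table 2 lists only race, age and marital status as Aim 1 patient-level data. This stands in part: the point applies to any such p-value, not to one the plan explicitly promises. But stage and grade are named primary outcomes, Table 2 counts t-tests among descriptive analyses, and the testing rule in B.2.e is general.

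**Selection also uses screening.** The opening of B.2 says the study will "select four neighborhoods in Philadelphia with the highest population-adjusted rates of late-stage PCa and the lowest rates of PCa screening". If screening is measured independently, this could dilute the effect. It was not simulated.

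**Not every Aim 1 comparison is inflated.** A reader might infer that all of them are. The race and SES results show otherwise.

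**Hypothesis 1a can fail.** A reader might infer that it cannot, or that forming the groups is what biases it. Neither holds. The correlation uses no grouping, and its rejection rate falls well below 100% with fewer areas or a weaker stage-death link. With a stage-death link present, it also detects an association that is real among individuals; the difficulty lies in reading it as a neighborhood effect.

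**Shared cases are not stated.** The registry fields listed in B.2.a include no vital status or cause of death. The mortality sources named are EpiQMS and the all-cause data in the CHDB. That deaths come from the same cases is an inference. Population death rates would also include men diagnosed before the window, which weakens the overlap.

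**Conclusion.** The concern holds for stage, grade and aggressiveness compared between high- and lower-risk areas in the cases that defined those areas. At tract level, the unit named in the definition, a significant result for advanced status is close to certain with no true difference, and very likely for stage alone. With a few large areas the inflation is smaller but still well above 5%. The sizes rest on the assumed number of areas, advanced share and equal populations; the circularity does not.

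For Hypothesis 1a the conclusion is conditional. If deaths come from the same registry cases, a significant correlation partly reflects the individual stage-death link and is weak evidence that neighborhoods differ. If they come from elsewhere, these figures do not apply directly.

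Nothing here undermines the choice of the four neighborhoods or the Aim 3 test. Nor does it show that real differences between areas are absent, only that these p-values cannot establish them.

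**What to change.** In B.2.e:

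1. Report stage, grade and aggressiveness by high- and lower-risk group descriptively, without p-values; or test them only in diagnosis years not used to define the groups. All five years can still be used to choose the study neighborhoods.
2. State the source of area-level prostate-cancer deaths for Hypothesis 1a.
3. If those deaths come from the same registry cases, either say that the correlation partly reflects the individual link between stage and death, or take percent advanced from one half of the cases (for example alternate diagnosis years) and deaths from the other half, then swap the halves and average.

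The first two items cost a few sentences, though testing in held-out years uses fewer cases. The split in item 3 needs deaths linked to cases, or at least to diagnosis year; the listed registry fields do not show that this is available, and it could not be run on published mortality rates alone. Its statistical price is a noisier exposure and a wider interval for Hypothesis 1a.
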